conferring benefit to Activities of Daily Living in people over 60 when the Reasoning CT was completed over six months⁸. Further analysis of the baseline data from this trial showed a clear age-related sensitivity in performance on reasoning tasks indicating that this aspect of cognition is particularly important in age-related cognitive health⁹. Recent analysis of data from a large online longitudinal study has indicated a potential training effect when older adults complete a Grammatical Reasoning task regularly. This raises the possibility of potential benefit with short-term, intensive training in this specific domain through one focussed task.

A novel online research infrastructure is available at King's College London and Exeter University which provides the opportunity to deliver online CT interventions to large numbers of older adults. The Platform for Research Online to investigate Cognition and Genetics in Ageing (PROTECT) is an online research study and longitudinal cohort of 20,000 people over 50. Participants provide demographic and lifestyle information and complete a battery of validated cognitive and mental health assessments annually. They also provide a DNA sample to enable genetic association work to be completed. PROTECT provides a unique platform for online clinical trial delivery. The website has been designed to enable nested interventions to be embedded into it, which participants are then invited to enrol for. This will provide a ready-made platform from which to evaluate the short-term impact of intensive training in Grammatical Reasoning in older adults.

Objectives

This study seeks to establish the effectiveness of an online short-term intensive Grammatical Reasoning training (START) intervention on cognition in adults over 50

Hypothesis

The underpinning hypothesis is that adults completing the START programme regularly over six weeks will show significant improvements to their reasoning and overall cognitive ability.

Methodology

Design: Six-month randomised controlled trial with a six week intervention period. Participants will be randomised to either the START intervention or to a control group for six weeks.

Participants: 7239 adults over 50

Setting: Intervention delivered online through the PROTECT website

Inclusion Criteria: Participants will: (i) Be over 50, (ii) Have access to a computer or device (smartphone / tablet etc) and the internet (iii) Be registered as a participant on the PROTECT website

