3. Verbal Learning, as measured through the validated Paired Associate Learning measure, which is highly sensitive to change in cognition and has been used to predict conversion to Alzheimer's Disease in people with cognitive impairment.
4. Activities of Daily Living, as measured by the modified IADL measure which is validated for use in this population, and has been successfully used to show change in IADL in previous online brain training studies.
5. Use of cognitive training: Participants will complete a brief question regarding their use of cognitive training (computer games, crosswords, Sudoku etc) and the regularity of use at each timepoint

Participants will be directed to complete these measures at baseline, two weeks and six weeks, using their 'My Study' homepage on the PROTECT website. Prompts to complete outcome measures will be sent out as automated emails.

Justification for sample size: The sample size calculation is based on the published study of online cognitive training in adults over 50 which showed significant benefit to reasoning, memory and function⁸. Based on an effect size of 0.11, 4826 participants would be required to provide 90% power at a two-sided 0.01 significance level. Assuming a conservative drop-out rate of 50%, a total of 7326 participants will be recruited.

Recruitment and Consent: Recruitment will be achieved through the PROTECT site through promotion of the study to existing participants. Additional publicity will be coordinated to drive recruitment to the PROTECT study overall, with a focus on enrolling new participants into the START trial. This recruitment will be supported by the Royal Devon & Exeter NHS Foundation Trust and the Devon Partnership NHS Trust. This approach has been used to great success during the launch of the previous cognitive training trial, which recruited over 15,000 people over 24 hours. Participants will consent to the study through the established PROTECT online consent process, which enables an electronic records of consent to be taken. Capacity to consent will be monitored as per the approved PROTECT protocol, which involves flagging of significant cognitive decline, an informant questionnaire and regular reminders that people with a diagnosis of dementia are not eligible to continue in the study.

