Randomisation: Participants will be randomly allocated to START or control groups via stratified randomisation algorithm embedded in the PROTECT website. Stratification variables will be age, gender and whether the participant was involved in a previous brain training study.

Participant Journey

1. Participants will be invited to take part in the START study via an email from the PROTECT study. Information will also be provided on the PROTECT homepage.
2. Participants will log into their PROTECT homepage and 'My Study' area. From here they will access an online version of the Participant Information Sheet, which will also be available for download.
3. Participants will provide consent to take part in the START study via the electronic consent form. This process is already in use in the PROTECT study, and requires participants to consent to each condition, and then to confirm their consent for a second time to avoid accidental consent.
4. Participants will be allocated a unique START study ID number and will be randomly allocated to either the START intervention or control
5. Participants will complete baseline assessments for cognition and Instrumental Activities of Daily Living. The cognitive test package will be provided by Wesnes Cognition, a partner website in the PROTECT study which provides validated online cognitive tests. The test battery will take up to 15 minutes to complete and will include tests of Paired Associate Learning, Pattern Separation, Simple Reaction Time, Choice Reaction Time and Digit Vigilance. The Instrumental Activities of Daily Living assessment will be completed on the PROTECT site. Participants will be prompted to complete their assessments on their individual 'My Study' web page.
6. Participants will be able to access their START training through their 'My Study' page. They will be encouraged to play the task three times a week, but they can play as often as they wish. Automated emails will encourage participants to log on and play every few days.
7. Participants will be prompted by email to log in and complete follow-up assessments after two weeks and six weeks.
8. At six weeks participants will receive an email to let them know that the training portion of the study has been completed.
9. Participants will be contacted a six months to ask them to complete the outcome assessment battery once more to evaluate long-term impacts.

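### The recruitment totals (7239 and 7326) do not cover the assumed 50% drop-out: on the plan's own calculation power is about 77%, not 90%, and the two totals disagree

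*Combined protocol and SAP*

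**What the plan says.** The section on justification for sample size gives the requirement: "Based on an effect size of 0.11, 4826 participants would be required", and the operating characteristics are "90% power at a two-sided 0.01 significance level". It then inflates for losses: "Assuming a conservative drop-out rate of 50%, a total of 7326 participants will be recruited".

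The Methodology section gives another total: "Participants: 7239 adults over 50". Nothing in the document explains the difference of 87.

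Two further points bear on this. The Data Analysis section restricts the primary analysis to complete cases and specifies linear regression adjusted for the baseline value of the outcome and the stratification variables. The sample size section gives no baseline–outcome correlation and claims no gain in precision from that adjustment.

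**The concern.** If half of those recruited are expected to be lost, the number to recruit is the number needed divided by the proportion retained. Neither stated total meets that: halving either one leaves well under 4826. The Methodology total equals 4826 plus 50% of 4826, which suggests that the drop-out percentage was added on rather than the requirement divided by 0.5. The documents do not say how either total was derived, so this is an inference. The shortfall does not depend on it.

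This is the trial's only power statement, and the Data Analysis section relies on it when it says that the trial is powered for the overall comparison and not for interactions. The assumed effect is small, so a non-significant result is a realistic outcome. A reader would set such a result against a planned type II error of 10%, when the plan's own assumptions imply about 23%. With two totals, the protocol also has no single recruitment target to report against. The type I error and the validity of the treatment estimate are not affected.

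**Working it through.** **Inputs.** From the sample size section: effect size d = 0.11, two-sided α = 0.01, power 90%, 4826 required, drop-out 50%, 7326 to recruit. From Methodology: 7239 participants. Assumed: 1:1 allocation (two arms, ratio not stated) and d as a standardised difference in an unadjusted two-sample comparison.

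**Step 1: reproduce 4826.** With z(0.995) = 2.576 and z(0.90) = 1.282:

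n per arm = 2 × [(2.576 + 1.282)/0.11]² ≈ 2459.4, rounded up to 2460, so 4920 in total.

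This is within 2% of 4826, which corresponds to d ≈ 0.111. Other readings fit worse: one-sided 0.01 gives 4304, two-sided 0.05 gives 3474, and 80% power gives 3862. So 4826 is a sound base figure, and the unadjusted formula is the reading that yields it.

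**Step 2: inflate for 50% drop-out.**

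- Dividing by the proportion retained: 4826/(1 − 0.5) = 9652.
- Adding 50%: 4826 × 1.5 = 7239, exactly the Methodology total.
- The other total: 7326/4826 = 1.518 and 7326/1.5 = 4884, which matches no stated input.

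**Step 3: completers, power and detectable effect.** For N analysed participants, power = Φ(d√(N/4) − 2.576), and the effect detectable with 90% power is 2 × (2.576 + 1.282)/√N.

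| Recruited | Analysed at 50% drop-out | Short of 4826 by | Power at d = 0.11 | Effect detectable with 90% power |
|---|---|---|---|---|
| 7239 | 3619.5 (about 3620) | about 1206 | 76.8% | 0.128 |
| 7326 | 3663 | 1163 | 77.4% | 0.127 |
| 9652 | 4826 | 0 | 89.3% | 0.111 |

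For 7239: 0.11 × √(3619.5/4) = 3.309; 3.309 − 2.576 = 0.733; Φ(0.733) = 0.768. A calculation from the non-central t distribution agrees (76.8% and 77.4%). If 0.11 is a rounded 0.111, power with 7239 recruited is still only about 78%.

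**Step 4: drop-out that the totals tolerate.** 1 − 4826/7239 = 33.3%; 1 − 4826/7326 = 34.1%.

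**Step 5: sensitivity to baseline adjustment.** If 0.11 is on the unadjusted scale, adjustment multiplies the residual SD by √(1 − r²), where r is the baseline–outcome correlation. The plan gives no r, so a range is shown, at 50% drop-out:

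| r | 7239 recruited | 7326 recruited |
|---|---|---|
| 0 | 76.8% | 77.4% |
| 0.3 | 81.4% | 82.0% |
| 0.5 | 89.3% | 89.8% |
| 0.7 | 98.0% | 98.2% |

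Reaching 90% needs r ≈ 0.51 at either total.

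**The case against.** The strongest objection is that 77% belongs to an analysis the trial will not run. The planned model adjusts for baseline, and with a correlation near 0.5 the 3620 completers would give the same power, 89.3%, that 4826 give unadjusted. This stands as a limit on the claim: 77% is what the plan's own sample size calculation delivers, and the planned regression may do better. It does not rescue the stated figure. The plan gives no correlation, takes no credit for one, and does not say whether 0.11 is already an adjusted effect, in which case there would be nothing further to gain.

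The plan also calls 50% conservative, so actual losses may be smaller. With 7239 recruited, unadjusted power would be 85.3% at 40% drop-out and 89.3% at one third. That is fair, but the text claims cover at 50%, which neither total gives.

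Three smaller points stand in part. Only 7239 shows the exact × 1.5 pattern; 7326 does not. People who stop training but complete the assessments stay in the intention-to-treat comparison, so the loss applies to those without outcome data, which is the natural meaning of drop-out in a sample size section. And the two totals differ by only 1.2%, or about 0.6 percentage points of power, so that discrepancy matters for consistency far more than for power.

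**Conclusion.** The concern holds. Neither recruitment total leaves 4826 analysable participants at the plan's own 50% drop-out; 9652 would be needed. On the plan's unadjusted calculation, with 1:1 allocation assumed, power is 76.8% to 77.4% and not 90%, a type II error of about 23%. The stated totals are consistent with 4826 completers only if drop-out is no more than 33.3% (7239) or 34.1% (7326). A baseline–outcome correlation of about 0.51, with 0.11 on the unadjusted scale, would restore 90%, but the plan makes no such case. The two totals contradict each other whichever assumptions are used. As written, the power statement is wrong and must be corrected.

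**What to change.** Use one total in both the Methodology and sample size sections, and state what it delivers. Any one of these would do:

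- **Restate the power.** For example: *N = 7239; at 50% drop-out about 3620 are analysed, giving about 77% power for an effect size of 0.11 at two-sided 0.01, and 90% power for 0.128.* If 7326 is the intended total, the figures are 3663, 77% and 0.127.
- **Restate the drop-out.** Say that 7239 tolerates 33% drop-out (7326 tolerates 34%), and justify that rate.
- **State the correlation relied on.** Give the baseline–outcome correlation with its source, confirm that 0.11 is on the unadjusted scale, and show the adjusted calculation. About 0.51 is needed for 90%.
- **Keep both 50% and 90%.** The matching total is then 9652 (9840 if starting from the recomputed 4920).

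The first three change only the wording and need no extra participants; the price of the first is a less favourable power statement. The fourth means 2413 more participants than 7239, or 2326 more than 7326. Whichever is chosen, add the allocation ratio, since the calculation depends on it.

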10. At the end of the study participants will receive a newsletter giving them information on the findings.

Data Analysis

The analysis and presentation of the trial will be in accordance with CONSORT guidelines. Recruitment, intervention uptake, outcome completion rates and drop out will be reported (with 95% CIs) as a flow diagram and the baseline participant characteristics in the intervention and control groups compared.

The primary analysis will undertake an intention to treat between group comparison of primary and secondary outcomes at six months post-randomisation using linear regression adjusting

for baseline outcome value and stratification and minimisation variables. The primary analysis will include complete case data only.

Additional analyses of the primary outcome will take three general forms. First, the influence of missing data will be investigated. As part of our approach to missing data, we will investigate which participant characteristics (including socio-demographic characteristics and baseline clinical values) are associated with primary and secondary outcome scores, and their propensity for missingness. Second, the effect of adherence with intervention will be investigated using allocation respecting methods such as complier averaged causal effects (CACE) modelling using instrumental variable regression. Third, interaction terms will be entered into the primary regression analyses in order to conduct pre-specified subgroup analyses that will include examining impact on groups with early deficits in reasoning, memory and executive function. These will be defined as participants performing outside of one SD of age-matched norms in the reasoning, memory and executive function tasks at baseline. Since the trial is powered to detect overall differences between the groups rather than interactions of this kind, the results of these exploratory analyses will be presented using confidence intervals, as well as a global p-value for the interaction between treatment and each variable, and interpreted with due caution.

No interim analyses are planned. A full analysis plan will be developed prior to completion of data collection and agreed with the Trial Steering Committee and the Data Monitoring and Ethics Committee. All analyses will be undertaken in STATA v.14.

Data Management

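### Participants are randomised before the baseline battery, so anyone who does not complete it drops out of the baseline-adjusted complete-case comparison

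*Combined protocol and SAP*

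**What the plan says.** The Participant Journey is a numbered sequence. Electronic consent is step 3. Step 4 is "Participants will be allocated a unique START study ID number and will be randomly allocated to either the START intervention or control". Step 5 is "Participants will complete baseline assessments for cognition and Instrumental Activities of Daily Living", done online without supervision: "Participants will be prompted to complete their assessments on their individual 'My Study' web page". Step 6 then says "Participants will be able to access their START training through their 'My Study' page".

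The Randomisation paragraph does not make a completed baseline a condition of allocation. It names the factors used: "Stratification variables will be age, gender and whether the participant was involved in a previous brain training study".

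Under Data Analysis, the primary comparison is described as intention to treat, by linear regression adjusting "for baseline outcome value and stratification and minimisation variables". The next sentence says "The primary analysis will include complete case data only". The exploratory deficit subgroups are "participants performing outside of one SD of age-matched norms in the reasoning, memory and executive function tasks at baseline".

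No other section gives a different order. The text does not say when participants learn their arm, does not describe masking, does not say that training stays closed until the baseline is submitted, and gives no rule for a randomised participant with no baseline value.

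**The concern.** In this sequence, having a baseline value is something that happens after randomisation, yet the primary analysis requires one. Anyone who consents, is allocated and then does not finish the battery counts as randomised but cannot enter the model. Two things are at stake.

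- **Power.** For a given number randomised, each such loss removes a participant from the primary analysis.
- **Validity.** If the proportion completing the baseline, or the way they perform on it, depends on the arm, the groups compared are no longer the groups randomised. The same applies to the deficit subgroups, whose membership is read from baseline scores.

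The planned effect is only 0.11 SD, so even a modest distortion would be a noticeable share of it. A baseline that was never collected cannot be recovered later.

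**Working it through.** **1. Order against analysis.** The journey runs consent (3), allocation (4), baseline (5), training (6). The model needs both a baseline and an outcome value for each participant. A participant lost between steps 4 and 5 is therefore randomised and excluded. This follows directly from the text.

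**2. When exclusion costs only power, and when it biases.** Measuring a covariate after allocation does not by itself bias a baseline-adjusted comparison. If completion and scores are unrelated to arm, the loss reduces numbers only. Bias needs either completion of the baseline, or scores on it, to differ by arm. The documents give no figure for either.

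**3. Inputs for the power illustration.** From the sample-size justification: effect 0.11, two-sided 0.01, 90% power, 4826 evaluable, 50% drop-out, 7326 recruited. (The Participants line under Methodology gives 7239.) The allocation ratio is not stated; 1:1 is assumed. The proportion *f* lost before baseline is not given; 0% to 30% is assumed.

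**4. The plan's own figure.** Per arm, n = 2(z₀.₉₉₅ + z₀.₉₀)²/d² = 2(2.5758 + 1.2816)²/0.11² = 2460, so 4920 in total. The stated 4826 is within 1.9% of this and gives 89.3% power, so it is reproduced closely enough.

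**5. Effect of loss before baseline, if it comes on top of the 50%.**

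Complete cases C = 7326 × (1 − f) × 0.5. Power = Φ(0.11 × √(C/4) − 2.5758). For f = 0: C = 3663 and 0.11 × √915.75 − 2.5758 = 0.753, which gives 77.4%. The last column is 4826/((1 − f) × 0.5).

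| f (assumed) | Complete cases from 7326 | Power | Randomised needed for 4826 complete cases |
|---|---|---|---|
| 0% | 3663 | 77.4% | 9652 |
| 10% | 3297 | 72.0% | 10725 |
| 20% | 2930 | 65.6% | 12065 |
| 30% | 2564 | 58.3% | 13789 |

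Starting from 7239, the powers are 76.8%, 71.3%, 64.9% and 57.6%.

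**6. Reading the table.** The fall from 89.3% to 77.4% in the first row is not due to the order of steps. It arises because the recruited total is about 4826 × 1.5 = 7239 and not 4826/0.5 = 9652, which is a separate matter. Only the falls below the first row belong to this point, and only if early losses are additional to the 50%. If the 50% already includes them, 77.4% stands. No allowance is made for precision gained from covariate adjustment.

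**The case against.** The strongest reply is that the same list puts the baseline (step 5) before training (step 6). A reader might infer from the shared My Study page, and from the absence of a stated lock, that START participants will play before their baseline and that adjustment will then subtract part of the effect. The documents do not support that. Silence about a lock is not evidence that training opens early, and taking the list at its word excludes early play.

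A size could be attached to that inference through bias = −slope × baseline shift. Shifts of 0.02 to 0.05 SD with slopes of 0.5 to 0.7 give 0.010 to 0.035 SD, or 9% to 32% of 0.11. But neither the shifts nor the slopes come from the documents, and a shift of zero gives no bias. If knowing one's arm raised motivation at both baseline and follow-up, adjustment would partly remove an expectancy effect, not a training effect.

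A reader might also infer that the randomised comparison is broken. That is not shown either:

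- The control arm has an active task intended to match engagement, which argues against a large difference in completion.
- The 50% drop-out may already include people who never start.
- Existing PROTECT members have annual cognitive data.
- The planned flow diagram and missing-data work would help to expose unequal losses.
- The subgroup analyses are labelled exploratory.

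All of this stands, and it limits the size and certainty of the harm. It does not remove the point that the stated order lets people be randomised and then excluded for want of a baseline. Reporting such losses does not prevent them, and the plan does not say that earlier PROTECT scores would stand in for a missing baseline.

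**Conclusion.** The point holds as a design weakness that is worth correcting because correction is cheap. Allocation precedes a self-directed baseline, the primary model needs that baseline, and the text neither masks allocation nor makes training conditional on completing it. Loss of power for a fixed number randomised is certain if anyone fails to complete the baseline. Its amount is unknown, and the 72.0% to 58.3% range rests on assumed losses of 10% to 30% added to the 50%, with 1:1 allocation. Bias in the main comparison or the subgroups is possible only if completion or scores differ by arm, and the documents give nothing from which to size it. Contamination of the baseline by training is not shown. This should be fixed, but the documents do not make it a defect that invalidates the trial.

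**What to change.** Swap steps 4 and 5. The website should run the stratified allocation only after the baseline cognitive battery and the daily-living measure have been submitted, and should open the training page only after allocation. The algorithm need not change: age, gender and involvement in a previous brain training study do not depend on the START battery. Data Analysis also mentions minimisation variables, but none is named; if any exists, it should be listed and its source checked.

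If the website already works in this order, the protocol text should be corrected to say so. If allocation has to stay at step 4, the protocol should state that the arm is not shown and training stays closed until the baseline is submitted, and the analysis plan should state how a randomised participant without a baseline is handled. In either case the flow diagram should show the number lost before baseline.

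The cost is a change of website sequence and more consents per randomised participant. The swap does not recover people who stop before the baseline. It moves them out of the randomised total, and under the current order they would not have entered the planned primary analysis anyway.

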Exclusion Criteria: Participants will be excluded if they have an established diagnosis of dementia.

Intervention: The START intervention consists of a Grammatical Reasoning cognitive task delivered online by Wesnes Cognition. This task measures how well the participant can mentally reason the relationships among different shape combinations assigned to grammatical statements. The shapes are a circle and a square, on each trial the square can either be contained within the square, or vice versa. The difficulty of each problem depends on the grammatical statement presented. There are 32 trials in total, 16 being simple questions (e.g. 'the circle is bigger than the square', 'the square contains the circle') and 16 more grammatically complex questions (e.g. 'the circle is not bigger than the square; 'the square does not contain the circle'). Half of each type of trial required the answer YES, and the other

half NO. These responses are made by pressing the left keyboard arrow key for NO and the right keyboard arrow key for YES. Accuracy and speed are recorded for each trial. The task takes around three minutes to complete. Participants will be encouraged to complete the START training once a day for the six-week period of the study

The control group will complete a basic picture-matching task that will provide the same level of engagement, but without the learning effects¹⁰.

Outcome Measures:

The primary outcome measure will be a composite measure of cognitive function, created through a combined score of each of the measures described below, as measured at six weeks. The individual measures will be included as discrete secondary outcome measures. All outcome measures will be completed online. They are sensitive to change in cognition, and validated for use in older adults to detect early changes in cognition.

1. Executive function, as measured by two tests of visual attention and task-switching, the Trailmaking B and the Switching Stroop Test which are validated measures of use in this population.
2. Cognitive function, as measured through the Wesnes Cognition Ltd CogTrack™ system. Individual measures are: Baddeley Logical Reasoning Task (letter sequence)¹¹, Digit Vigilance, Simple and Choice Reaction time, Spatial Working Memory, Numeric Working Memory, Pattern Separation, Word Recall (delayed and immediate) and Word Recognition.

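### The primary outcome is defined at six weeks, but the only primary between-group analysis specified is at six months, so the defined endpoint has no stated primary comparison

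*Combined protocol and SAP*

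**What the plan says.** Four parts of the combined protocol and SAP bear on the primary time point.

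- **Outcome Measures** makes the primary outcome a composite cognitive score, "created through a combined score of each of the measures described below, as measured at six weeks". The schedule at the end of that section reads "Participants will be directed to complete these measures at baseline, two weeks and six weeks". It does not list six months.
- **Data Analysis** describes the primary analysis, by intention to treat, as a "between group comparison of primary and secondary outcomes at six months post-randomisation". It uses linear regression adjusted for the baseline value and the stratification variables, and adds: "The primary analysis will include complete case data only".
- **Participant Journey** has training end at six weeks (step 8). At six months participants are contacted "to ask them to complete the outcome assessment battery once more to evaluate long-term impacts" (step 9).
- **Hypothesis and Design** state that "adults completing the START programme regularly over six weeks will show significant improvements to their reasoning and overall cognitive ability", and describe the study as a "Six-month randomised controlled trial with a six week intervention period".

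The sample-size paragraph gives no time point for its effect size or its drop-out rate. Data Analysis promises a fuller analysis plan, to be agreed with the two oversight committees before data collection is complete. That plan is not among the documents.

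**The concern.** The time point is part of the definition of a primary endpoint. Here the outcome definition and the analysis sentence give different ones, and both cannot be followed. No section specifies a between-group comparison at six weeks.

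The two time points answer different questions: whether the training works by the time it ends, and whether any effect lasts about 4.5 months without it (six months less roughly one and a half). The answers could differ. While the text supports either, the primary result could be settled after the data are known. The subgroup analyses are built on the primary regression and inherit the ambiguity. So does the complete-case set, because those with complete data at six weeks need not be those with complete data at six months.

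**Working it through.** **1. Does the sample-size calculation show which time point was powered?**

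Inputs from the sample-size paragraph: standardised effect 0.11, two-sided alpha 0.01, power 90%, stated requirement 4826. The allocation ratio is not stated; 1:1 is assumed.

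n per arm = 2 × (z₀.₉₉₅ + z₀.₉₀)² / d² = 2 × (2.5758 + 1.2816)² / 0.11² = 2 × 14.88 / 0.0121 ≈ 2460, or 4920 in total.

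This is 1.9% above 4826. An unrounded effect of about 0.111 gives 4832, so rounding of the effect size can account for the gap. Power at 4826 is 89.3%. The stated figure therefore reproduces, but nothing in the formula depends on time, so it cannot say which comparison was powered.

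**2. Which way does the text lean?**

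| Place | Points to |
|---|---|
| Outcome Measures, primary outcome definition | six weeks |
| Outcome Measures, schedule | six weeks (last visit listed) |
| Hypothesis | six weeks of training |
| Participant Journey, steps 8 and 9 | six weeks as end of training; six months as long-term follow-up |
| Data Analysis, primary analysis | six months |
| Design | six-month trial length; compatible with either |
| Sample size | silent |

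The balance favours six weeks, but the analysis sentence is explicit and the trial is described as lasting six months.

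**3. What is the error rate if either time point could be claimed?**

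With two tests at 0.01 each:

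- Independent: 1 − (1 − 0.01)² = 0.0199.
- Correlated: 1 − P(|Z₁| < 2.576 and |Z₂| < 2.576) for a bivariate normal with correlation ρ.

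| Assumed ρ | Type I error |
|---|---|
| 0 | 0.0199 |
| 0.5 | 0.0190 |
| 0.7 | 0.0177 |
| 0.9 | 0.0149 |

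The same composite in largely the same people will give positively correlated tests, so 0.0199 is a ceiling. A range of about 1.5 to 1.9 times the nominal level is more realistic. The documents give no correlation; these values are assumptions.

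**The case against.** The strongest reply is that the plan does not set out two primary tests. It has one endpoint and one primary analysis that disagree on timing, and nowhere says that success may be claimed at either. A fuller analysis plan is promised and no interim analysis is planned, so a choice made after seeing the data is a risk and not a feature of the design. This stands, and the error rates above are conditional on it. It does not remove the contradiction. The promised plan cannot be credited unseen, it would have to overrule one of the two sentences, and it is due only before data collection is complete, when six-week data may already exist.

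Three stronger readings are tempting and are not supported:

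- **That the six-week outcome is never analysed.** The additional analyses (missing data, adherence, subgroups) name no time point and could be read as six-week analyses. What is missing is a primary six-week comparison.
- **That a six-month primary analysis would lose a calculable amount of power.** More attrition by six months is plausible, but the documents give no retention by time point. The 50% drop-out is undated and, in a six-month trial, may already be the six-month figure. Power at 50% drop-out is 76.8% with 7239 recruited (Participants) or 77.4% with 7326 (sample-size paragraph). That shortfall reflects a separate recruitment problem: 4826 × 1.5 = 7239, whereas 50% drop-out needs 4826 / 0.5 = 9652. It says nothing about timing.
- **That a six-month comparison would not test the hypothesis.** The six weeks in the hypothesis describe the training period, not the time of measurement. Six months is a weaker fit, not a failure to test it.

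**Conclusion.** The contradiction is real and should be corrected before any outcome data are seen. The primary endpoint is defined at six weeks, its only specified primary comparison is at six months, and two candidate primary comparisons are left open.

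The size that can be given is conditional. If either time point could carry the claim at 0.01, the type I error is at most 0.0199, and about 0.019 to 0.015 at assumed correlations of 0.5 to 0.9. No figure for lost power at six months can be drawn from the documents. Six weeks is the better-supported reading, but the six-month design description means that the sponsor has to confirm it.

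**What to change.** 1. In Data Analysis, change the time of the primary comparison from six months to six weeks after randomisation, subject to the sponsor's confirmation, so that it matches Outcome Measures.
2. Label the six-month comparison as a secondary analysis of persistence, using the same regression model.
3. Add six months to the schedule in Outcome Measures, to agree with Participant Journey step 9. This is tidying, since the visit is already planned.

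If the sponsor confirms six months as primary, the outcome definition must change, the schedule must list six months, and the six-week comparison becomes secondary.

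The cost is a short wording amendment. Both assessments are already planned, and naming one time point leaves the evaluable sample size unchanged. Keeping both as primary would not be free: with Bonferroni at 0.005 each, the same formula needs 5528 evaluable participants for 90% power per test, and 4826 would give 84.5% per test, assuming an effect of 0.11 at both time points.
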